## 7.2.2. Photographic Imaging

Digital photographic images of CMP-001 target and non-target skin lesions, including caliper measurements of superficial cutaneous lesions, will be obtained per the time points specified in the Schedule of Assessments (Table 1). Photos should be taken with a digital camera of adequate resolution according to the imaging guideline. To clearly capture the morphology of the tumor, both the skin lesion and the surrounding tissue must be included in the field of view. Each lesion should be clearly labeled with a unique identifier which must be used throughout the trial. A metric ruler must also be included in the photograph field of view as a size reference.

If a CR is observed, sites should continue to obtain confirmation photographs according to the Schedule of Assessments (Table 1).

Refer to the Imaging Guideline for further guidance.

## 7.2.2.1. Central Nervous System Imaging

Baseline brain imaging by contrast-enhanced CT or MRI (per site local standards) must be provided at Screening. Subsequent brain imaging is only required for subjects with current or prior history of brain metastases or clinical signs or symptoms of CNS disease. The same modality of brain imaging should be utilized throughout the study for an individual subject.

#### 7.2.3. On-Treatment Disease Assessment

On-treatment disease assessments will be collected per the time points specified in the Schedule of Assessments (Table 1).

Amendment 1 (Version 2.0) 04 February 202164

Confidential

The volume and inflammation from an IT injection of CMP-001 may cause a tumor to transiently enlarge leading to an inaccurate assessment. All scans should be performed predose and at least 2 weeks after a previous CMP-001 IT injection to prevent injection-related pseudoprogression.

## 7.2.3.1. Disease Assessment Beyond Progressive Disease

Subjects with PD per RECIST v1.1 as determined by Investigator assessment should remain on treatment per Investigator discretion and have a follow-up scan performed at least 4 weeks after the initial date of PD to confirm progression per RECIST v1.1. Subjects who receive study treatment beyond PD per RECIST v1.1 will have subsequent disease assessments evaluated using iRECIST by the Investigator. Disease assessments should continue according to the Schedule of Assessments (Table 1).

## **7.2.3.2.** Confirmation of Response

Subjects with a CR or PR per RECIST v1.1 or iCR or iPR per iRECIST as determined by Investigator assessment must have a confirmatory assessment at least 4 weeks after the initial response. All scans should be performed at least 2 weeks after the previous CMP-001 injection to prevent injection-related pseudoprogression.

Once confirmed, subsequent assessments should continue according to the Schedule of Assessments (Table 1).

### 7.3. Translational Assessments

## 7.3.1. Collection of Blood for Translational Biomarker Analyses

Blood samples, including serum and/or plasma, will be collected for exploratory assessments during the Phase 2 portion of the study as specified in the Schedule of Assessments (Table 1). The procedures for sample collection, processing, storage, and shipment are provided in the Laboratory Manual. Blood samples will be tested to determine concentration of CXCL10 before and during treatment with CMP-001 to evaluate association with the observed clinical responses to study treatment. Samples may be used for additional exploratory analysis of biomarkers thought to play a role in melanoma, cancer immunotherapy, or TLR9, including but not limited to concentration of serum/plasma analytes. These findings may be analyzed for association with observed clinical responses to the combination of CMP-001 and nivolumab and subsequent exploration of factors associated with response or resistance to CMP-001 in combination with nivolumab. These samples may be also used for research to develop methods, assays, prognostics, and/or companion diagnostics related to TLR9 agonism and cancer immunotherapy.

## 7.3.2. Collection of Tumor Biopsies for PD-L1 Staining and Translational Analyses

Determination of PD-L1 expression is required to confirm subject eligibility.

Fresh tumor biopsy samples are mandatory, if safe and medically feasible, as specified in the Schedule of Assessments (Table 1). If in the Investigator's opinion it is unsafe to perform a new biopsy, archival material must be used for analysis of PD-L1 expression. The decision and rationale to forego biopsy samples at Screening or during the treatment period should be clearly documented. Archival tumor biopsy samples should also be collected during Screening, if available.

Tumor biopsies will be used to assess PD-L1 expression and may be used to analyze tumor immune cell infiltrates, such as CD3+CD8+ T cells. Biopsies may be used for additional exploratory analysis of biomarkers thought to play a role in melanoma, cancer immunotherapy, or TLR9, including but not limited to RNA analyses to monitor gene expression and DNA analyses to identify mutations associated with cancer. These findings may be analyzed for association with observed clinical response, resistance, and/or AEs to the combination of CMP-001 and nivolumab.

Additional tumor biopsies may be collected during the study at the discretion of the Investigator.

## 7.4. Safety Assessments

Safety will be assessed on an ongoing basis throughout this study. All safety assessments and AEs will be recorded on the appropriate eCRF and reported to the Sponsor or its representatives (as applicable). All AEs/SAEs will be assessed continually from the time of informed consent through 100 days after the last dose of study treatment (both CMP-001 and nivolumab) or until an alternative cancer treatment is initiated, whichever occurs first, for all subjects. All other medical occurrences (non-adverse events) that begin before the start of study treatment should be recorded on the Medical History/Current Medical Conditions section of the eCRF, not the AE section. All AEs reported on or after the date that study treatment was first administered (W1D1), will be recorded on the eCRF and will be considered treatment-emergent adverse events (TEAEs). All TEAEs, defined as an AE that started or worsened in severity on or after the date that study treatment was first administered (W1D1), will be graded according to CTCAE v5.0 (Appendix C) and coded using Medical Dictionary for Regulatory Activities (MedDRA). Worsening TEAEs (ie, increase to higher severity/grade) should be recorded as new AEs. Ongoing AEs with a decrease in severity/grade do not need to be captured as new AEs. Subjects who discontinue CMP-001 but remain on treatment with nivolumab will continue to have AEs collected according to this schedule until 100 days after the last dose of nivolumab or until an alternative cancer treatment is initiated, whichever occurs first.

Abnormal vital sign measurements, clinical laboratory test results, and/or physical examination findings deemed clinically significant by the Investigator may be repeated, until the value returns to Baseline, within normal limits (WNL), or reaches a clinically stable endpoint, as determined by the Investigator. Any post-Baseline abnormal findings that are considered clinically significant by the Investigator will be recorded on the AE page of the eCRF. The Investigator is responsible for reviewing all clinical laboratory results.

Additional measures, including non-study required laboratory tests, should be performed as clinically indicated or to comply with local regulations. Laboratory toxicities (eg, suspected drug-induced liver enzyme evaluations) will be monitored during the follow-up phase via on-site/local laboratories until all study treatment-related toxicities resolve, return to Baseline, or are deemed irreversible.

If a subject shows cardiac- or pulmonary-related signs (hypoxia, abnormal heart rate, or changes from Baseline) or symptoms (eg, dyspnea, cough, chest pain, fatigue, palpitations), the subject should be immediately evaluated to rule out cardiac or pulmonary toxicity.

Some of the assessments referred to in this section may not be captured as data in the eCRF. They are intended to be used as safety monitoring by the treating physician. Additional testing or assessments may be performed as clinically necessary or where required by institutional or local regulations.

Any incidental findings of potential clinical relevance that are not directly associated with the objectives of the protocol should be evaluated and handled by the Study Investigator as per standard medical/clinical judgment.

#### 7.4.1. Adverse Events

AEs will be assessed continually from the time that the informed consent is signed through 100 days after the last dose of study treatment (both CMP-001 and nivolumab) or until an alternative cancer treatment is initiated, whichever occurs first, for all subjects. Subjects who discontinue CMP-001 but remain on treatment with nivolumab will continue to have AEs collected according to this schedule until 100 days after the last dose of nivolumab or until an alternative cancer treatment is initiated, whichever occurs first. All AEs from the time that the informed consent is signed will be captured on the eCRF.

Treatment-related SAEs starting more than 100 days after the last dose of study treatment will be recorded on the AE eCRF.

Immune-mediated AEs (IMAEs) are AEs consistent with an immune-mediated mechanism or immune-mediated component for which noninflammatory etiologies (eg, infection or tumor progression) have been ruled out. IMAEs can include events with an alternate etiology which were exacerbated by the induction of autoimmunity. Information supporting the assessment will be collected on the subject's case report form.

See Section 8.3 for a full description of the collection and reporting of AEs during this study.

## 7.5. 100-Day Follow-up Contact

The 100-Day Follow-up contact is a safety follow up that may be conducted in the study clinic or via phone and should occur 100 days (+7) after the EOT or until an alternative cancer treatment is initiated, whichever occurs first. The subject should be questioned for any new AEs, resolution of prior AEs, and use of concomitant medications, including other cancer treatments. No other safety assessments are required unless the Investigator identifies a new safety concern that requires further follow-up.

# 7.6. Post-treatment Follow-up

Subjects who discontinue study treatment and transition into PTFU will continue to have disease assessments collected per the time points specified in the Schedule of Assessments (Table 1). Post-treatment follow-up disease assessments will continue until disease progression, initiation of another cancer treatment, death, loss to follow-up, withdrawal of consent, or End of Clinical Trial.

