Abbreviations: 100DFU = 100-day follow-up; AE= adverse event; CNS = central nervous system; CR = complete response; CT = computed tomography; D/d = day; ECG = electrocardiogram; ECOG = Eastern Cooperative Oncology Group; EOT = End Of Treatment; FSH = follicle stimulating hormone; iRECIST = immunotherapy Response Evaluation Criteria in Solid Tumors; iCR = immune complete response; INR = international normalized ratio; iPR = immune partial response; IT = intratumoral; LTSFU = Long-Term Survival Follow-up; MRI = magnetic resonance imaging; N/A = not applicable; PD-L1 = programmed cell death protein ligand 1; PET = positron emission tomography; PR = partial response; PT = prothrombin time; PTFU = Post-treatment Follow-up; PTT = partial thromboplastin time; RECIST = Response Evaluation Criteria in Solid Tumors; Q3mo = every 3 months; Q3W = every 3 weeks; Q6W = every 6 weeks; SC = subcutaneous; SAE = serious adverse event; W = week; WOCBP = women of child bearing potential.

- a. End of Treatment assessments to be performed within 7 days following subject discontinuation from the last study treatment (either CMP-001 or nivolumab). Removal of a subject from CMP-001 treatment is defined as the time in which the Investigator decides to discontinue study treatment. If a subject has CMP-001 dosing withheld for more than 3 consecutive doses for any reason during the Q3W dosing period, resumption of treatment must be discussed with the Medical Monitor, otherwise, the subject will be discontinued from study treatment and will have all EOT assessments performed.
- b. The 100DFU is a safety follow-up visit that may be conducted at the study site or via phone. This visit should occur 100 days (+7) after the EOT.
- c. Post-treatment Follow-up (PTFU) will be conducted every 3 months (± 2 weeks) for all subjects who discontinue study treatment but have not met criteria for study discontinuation. These subjects should remain on study and receive disease assessments every 3 months, until discontinuation.
- d. Long-Term Survival Follow-up (LTSFU) will be conducted every 3 months (± 4 weeks) after the EOT visit or the last disease assessment date in PTFU and may occur via phone.

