# 2.4. Phase 3 Study Endpoints

## 2.4.1. Phase 3 Primary Endpoint

The primary endpoint in the Phase 3 portion of the study is PFS defined as the time from the date of randomization to first date of documented progressive disease based on RECIST v1.1 by BICR or death from any cause, whichever occurs first.

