Subjects may continue to receive study treatment beyond progressive disease (PD) according to RECIST v1.1 and will be evaluated by the Investigator according to iRECIST. Subjects with PD per RECIST v1.1 as determined by Investigator assessment should remain on treatment per Investigator discretion and have a follow-up scan performed at least 4 weeks after the initial date of PD to confirm progression per RECIST v1.1.

Subjects who discontinue study treatment should complete an end of treatment (EOT) visit and 100-day safety follow-up contact, which should occur 100 days (+7) after EOT or until an alternative cancer treatment is initiated, whichever occurs first. Subjects who are post-treatment but have not met criteria for study discontinuation should remain on study for post-treatment follow-up (PTFU) and long-term survival follow-up (LTSFU) and receive study evaluations for efficacy according to the Schedule of Assessments (Table 1).

At the end of the treatment period (2 years), the Sponsor will not continue to provide supplied study treatment to subjects/investigators unless the Sponsor chooses to extend the study. The Investigator should ensure that the subjects receive appropriate standard of care to treat the condition under study.

The study design for is summarized in Figure 1.

Figure 1: CMP-001-011 Study Schema

Abbreviations: 100DFU = 100-Day Follow-up; EOT = End of Treatment; LTSFU = Long-Term Survival Follow-up; IT = intratumoral; IV = intravenous; PTFU = Post-treatment Follow-up; Q3W = every 3 weeks; Q6W = every 6 weeks; Q12W = every 12 weeks; QW = weekly; W1D1 = Week 1 Day 1; W10D1 = Week 10 Day 1.

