## 4.5. Treatment Discontinuation

Treatment discontinuation is defined as any subject who stops receiving study treatment and does not restart within 12 weeks. Subjects who permanently discontinue (for >12 weeks) CMP-001 or nivolumab may not be re-treated with the discontinued study treatment in this study. When nivolumab is permanently discontinued due to an immune related AE, CMP-001 must also be permanently discontinued.

Treatment with study treatment should continue until one of the following occurs:

- Unacceptable AE that precludes further study treatment
- 2 years of study treatment
- PD per RECIST v1.1; continuation of treatment through suspected pseudoprogression is permitted at the Investigator's discretion until confirmed PD per iRECIST
- Upon request of the Sponsor or regulatory agency
- Clinical disease progression in the opinion of the Investigator
- If medically necessary in the opinion of the Investigator
- Subject withdraws consent for study treatment
- Subject has received study treatment for 2 years
- Subject becomes pregnant or begins breastfeeding

- Subject is lost to follow-up
- Death
- End of Clinical Trial

If a subject achieves and maintains a confirmed CR or iCR by Investigator assessment, IT or SC injections of CMP-001 or the combination of CMP-001 and nivolumab may be discontinued at the Investigator's discretion once the subject meets both of the following criteria:

- Subject has been treated for at least 48 weeks (the maximum duration of study treatment is 2 years)
- Subject has received at least 3 doses of assigned treatment beyond the date of the initial CR/iCR

Subjects with PD per RECIST v1.1 as determined by Investigator assessment should remain on treatment and have a follow-up scan performed at least 4 weeks after the initial date of PD to confirm progression per RECIST v1.1 by BICR.

Subjects who discontinue study treatment should complete an EOT visit and 100-day safety follow-up contact, which should occur 100 days (+7) after the EOT or until an alternative cancer treatment is initiated, whichever occurs first (Table 1). Subjects who discontinue study treatment for reasons other than disease progression (either per RECIST v1.1 or iRECIST by Investigator assessment) should remain on study for PTFU (Section 7.6) and receive disease assessments according to the Schedule of Assessments (Table 1).

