## **5.1.6.** Blinding and Unblinding Process

This is an open-label study.

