All events of RECIST v1.1 disease progression or death will be counted regardless of whether the event occurs while the subject is on study treatment or previously discontinued the study treatment. Subjects who do not experience disease progression or death as of the analysis cutoff date or final database lock will be censored at the date of the last adequate tumor assessment. Date of censoring for these subjects will be based on the last tumor assessment prior to missing the assessments. Censoring rules are summarized in Table 1. If a subject meets the criteria for more than one censoring rule, PFS will be censored at the earliest censoring date. Unless specified otherwise, the analysis methods described for DOR will be used for PFS. Additionally, the analysis of PFS based on RECIST v1.1 as determined by Investigator assessment will also be performed.

Overall Survival (OS). Overall survival will be calculated as the time from the date of randomization to the date of death due to any cause. Subjects who are alive or lost to follow-up as of the analysis cutoff date will be censored at the time of the last study contact date (i.e., date of last known alive). The last contact date will be derived as detailed in Table 2.

Based on these considerations, OS will be calculated as follows: OS (months) = (Death or Censoring Date – Date of Randomization + 1) / 30.4375

Regeneron Pharmaceuticals Inc. / Protocol: CMP-001-011 IQVIA Biotech (Confidential) Project # SZA58924

OS will be analyzed using the Kaplan-Meier method by treatment arm of the ITT Analysis Set. A Kaplan-Meier plot of OS will be generated for each treatment arm. The analysis methods described for DOR will be used for OS, unless specified otherwise.

Disease Control Rate (DCR). The confirmed disease control rate is defined as the proportion of subjects in each treatment arm in the analysis set who have a confirmed best response of CR, PR, or stable disease (SD) lasting at least 4 months. Per RECIST v1.1, CR or PR must be confirmed by a confirmatory assessment performed at least 4 weeks after the initial response. In the case of SD, measurements must have met the SD criteria at least once after study entry at a minimum interval of 6 weeks. Overall response assessment evaluated after subsequent new anti-cancer therapy will not be considered for DCR calculation.

DCR will be analyzed in a similar manner as ORR. Specifically, DCR and the associated 95% Clopper-Pearson CIs will be summarized.

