Death without PD per RECIST v1.1 and not receiving new anticancer therapy on/before data cutoff date	Event	Date of death	Death without PD per RECIST v1.1	X	
iCPD per iRECIST between scheduled disease assessments on/before new anticancer therapy or data cutoff date, whichever is earlier	Event	Earliest date of tumor assessment documenting iUPD	iCPD per iRECIST		X
Death without iCPD per iRECIST and not receiving new anticancer therapy on/before data cutoff date	Event	Date of death	Death without iCPD per iRECIST		X

Regeneron Pharmaceuticals Inc. / Protocol: CMP-001-011 IQVIA Biotech (Confidential) Project # SZA58924

Subjects with no post- baseline disease assessments	Censored	First Dose Date	No Adequate Disease Assessment per RECIST v1.1	PFS Only	
No PD per RECIST v1.1 or death as of data cutoff date and subject not received new anticancer therapy or received it after the data cutoff date	Censored	Date of last disease assessment on/before data cutoff date	Alive without Documented PD	X	
No PD per RECIST v1.1 or death as of data cutoff date and new anticancer therapy started before the data cutoff date	Censored	Date of last disease assessment prior to new anticancer therapy	Subsequent Anti- cancer Therapy without Documented PD	X	
PD per RECIST v1.1 or death after new anticancer therapy and the new anticancer started before data cutoff date	Censored	Date of last disease assessment prior to new anticancer therapy	Documented PD or Death after Subsequent Anti- cancer Therapy	X	
PD per RECIST v1.1 or death after new anticancer therapy and the new anticancer started after data cutoff date	Censored	Date of last disease assessment on/before data cutoff date	Documented PD or Death after Subsequent Anti- cancer Therapy	X	
PD per RECIST v1.1 or death immediately following two or more consecutive disease assessments since the last adequate disease assessment	Censored	Date of last adequate tumor assessment prior to the first missed assessment	PD or Death after Missing >= 2 Consecutive Disease Assessments	X	
Discontinuation from study before PD per RECIST v1.1 and death	Censored	Date of last adequate disease assessment	Discontinued from Study without Documented PD or Death	X	
iUPD per iRECIST at the time of PD per RECIST v1.1, continued study treatment without further tumor assessments as of data cutoff date	Censored	Date of the last tumor assessment on/before data cutoff date	No Adequate Disease Assessment per iRECIST		iPFS Only

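### The protocol contradicts itself on who is still scanned after treatment stops; on one reading imaging can end at the open-label Investigator's call of progression, although PFS and DOR rest on BICR progression

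*Protocol*

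**What the plan says.** **Endpoint.** Protocol 2.4.1 defines PFS to the "first date of documented progressive disease based on RECIST v1.1 by BICR or death from any cause, whichever occurs first". SAP IV.B keeps this definition as a secondary endpoint, and DOR also uses BICR progression. On masking, Protocol 5.1.6 states: "This is an open-label study".

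**Narrow follow-up rule.**
- Protocol 4.5: "Subjects who discontinue study treatment for reasons other than disease progression (either per RECIST v1.1 or iRECIST by Investigator assessment) should remain on study". What they remain for is post-treatment follow-up with its disease assessments.
- Protocol 7.6: "Post-treatment follow-up disease assessments will continue until disease progression, initiation of another cancer treatment, death, loss to follow-up". The list closes with consent withdrawal and End of Clinical Trial. No assessor is named.

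**Broad follow-up rule.**
- Protocol 3.1, with the same rule in the Synopsis: "Subjects who are post-treatment but have not met criteria for study discontinuation should remain on study for post-treatment follow-up (PTFU").
- Table 1 note c, on the same group: "These subjects should remain on study and receive disease assessments every 3 months, until discontinuation".
- Protocol 4.6 lists four reasons for leaving the study: withdrawal of consent, loss to follow-up, death and End of Clinical Trial. Progression is not one of them.

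**Confirmatory scan.** Section 4.5 asks for a scan at least 4 weeks after Investigator progression so that BICR can confirm it. Sections 3.1 and 7.2.3.1 repeat the scan, but they do not mention BICR and they leave staying on treatment to the Investigator.

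**SAP VIII.A.** The PFS text says "All events of RECIST v1.1 disease progression or death will be counted regardless of whether the event occurs while the subject is on study treatment"; events after treatment has stopped are likewise included. SAP Table 1 censors a subject without BICR progression or death at the last disease assessment. It also censors "PD per RECIST v1.1 or death immediately following two or more consecutive disease assessments since the last adequate disease assessment", with missed assessments given as the reason.

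**The concern.** Two sites could each follow the protocol and scan the same subject differently. Under the narrow rule, the person who decides whether scanning goes on knows the treatment arm, while the endpoint is read by a blinded committee that can only read the scans it receives.

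The exposed subject is the one with Investigator progression and no BICR progression by the last scan. That subject is censored. If he or she then dies without new therapy, the missed-assessment row can censor the death too, although the protocol itself ended the scans. That runs against the stated aim of counting events on or off treatment.

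Subjects whom an Investigator judges to be progressing are unlikely to have the same outlook as those who stay under observation. Censoring them is then informative and tends to lengthen BICR PFS and DOR. If the loss differs by arm, the comparison shifts too. Injection-related pseudoprogression, which the protocol warns of and which only Arm A can have, is one reason why Investigators' calls might differ by arm.

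**Working it through.** **1. The passages side by side, for one subject.** Investigator calls progression, BICR does not, treatment stops.

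| Source | Scanned afterwards? |
|---|---|
| Table 1 note c, Synopsis, 3.1, with 4.6 | Yes, every 3 months; progression is not a reason to leave the study |
| 4.5 | Not admitted to imaging follow-up, apart from the one confirmatory scan |
| 7.6 | Ends at progression, assessor unstated |
| SAP Table 1, alive | Censored at last assessment |
| SAP Table 1, later death without new therapy | An event under the death row; censored if the stopped scans count as missed |

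**2. Weight of one subject.** SAP II.C gives 9 subjects in Arm A and 11 in Arm B: 1/9 = 11%, 1/11 = 9%.

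**3. Effect on a median (illustration).** The documents give no discordance rate, so a loss fraction d of 10% to 30% is assumed. Other assumptions:
- BICR PFS is exponential with median 6.9 months, the top of the single-agent range in Protocol 1.1, so λ = ln 2 / 6.9 = 0.1005 per month.
- Each lost subject is censored 1.4 months (one 6-week scan interval) before BICR progression would have appeared.
- The confirmatory scan captures none of them.

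At time t the observed event density is (1−d)λe^(−λt), and the proportion at risk is (1−d)e^(−λt) + d·e^(−λ(t+1.4)). The observed hazard is therefore constant, and

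Kaplan-Meier median = 6.9 × [1 + (d/(1−d)) × e^(−1.4λ)], with e^(−1.4λ) = 0.869.

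| d | Formula | Simulation (200,000 subjects) |
|---|---|---|
| 0 | 6.90 | 6.88 |
| 10% | 6.9 × (1 + 0.111 × 0.869) = 7.57 | 7.56 |
| 20% | 6.9 × (1 + 0.250 × 0.869) = 8.40 | 8.38 |
| 30% | 6.9 × (1 + 0.429 × 0.869) = 9.47 | 9.41 |

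If the confirmatory scan captured half of the discordant subjects (assumption), 10% and 20% discordance become d = 5% and 10%, with medians 7.22 and 7.57. If it captured 80%, d = 2% and 4%, with medians 7.02 and 7.15.

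**4. Effect on the hazard ratio (illustration).** Let lost subjects be censored when BICR progression would have occurred. With exponential times, each arm's estimated rate is then multiplied by (1−d), so observed HR = true HR × (1−d_A)/(1−d_B).
- Equal loss: 0.70 stays 0.70.
- 10% in Arm A, 20% in Arm B: 0.70 × 0.9/0.8 = 0.79 (simulated 0.785).
- 20% in Arm A, 10% in Arm B: 0.70 × 0.8/0.9 = 0.62 (simulated 0.623); from a true HR of 1.0, 0.89.

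**5. The protocol's own PFS figure.** Schoenfeld's formula gives 4 × (1.960 + 1.282)² / (ln 0.70)² = 330.4, so 331 events, as stated in Protocol 9.1. The point does not depend on this number.

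**The case against.** **Scans do not simply stop.** A reader might infer that Investigator progression ends all imaging, so that BICR progression can never be seen. The documents do not support that. Section 4.5 asks for a further scan for BICR, and 7.2.1 sends additional imaging, including unscheduled scans, to BICR. This stands, and it is why the medians at a given loss are upper bounds. What remains is that the safeguard is one scan, that 3.1 and 7.2.3.1 state it without BICR, and that nothing in 4.5 or 7.6 continues imaging if BICR still disagrees.

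**No bias towards CMP-001 follows.** The likely patterns are readier calls of progression on monotherapy or restraint in Arm A. Both would censor more control subjects, lengthen control PFS and work against CMP-001. Only the reverse pattern favours CMP-001, and nothing in the documents makes it the likelier one.

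**Part of it will be visible anyway.** The SAP plans Investigator PFS, tabulates censoring reasons and lists response assessments. This stands, but none of it settles the status of a death after protocol-stopped scans.

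**The SAP conflict is partly one of interpretation.** The sentence on counting events concerns treatment status, and the same paragraph refers to Table 1 for censoring. A scan that was never due need not count as missed. Agreed; the table should say so.

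**Precision is poor.** Under the same exponential assumption without censoring, the sample median's 95% range is about 2.3 to 15.3 months with 9 subjects and 2.7 to 14.6 with 11. A shift of 0.7 months is small beside that.

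**Conclusion.** The contradiction between 4.5/7.6 and note c, the Synopsis, 3.1 and 4.6 is plain on the text, and so is the mismatch between an Investigator-based stop and a BICR-based endpoint. The consequence is a risk of informative censoring of BICR PFS and DOR. It cannot be called a measured loss, because no discordance rate is given.

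Under the stated assumptions the median is overstated by at most about 0.7, 1.5 and 2.5 to 2.6 months at 10%, 20% and 30% loss, and by less to the extent that the confirmatory scan works. The hazard ratio moves only if the loss differs by arm.

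A reader might also infer that a confirmatory test is at stake, since above 1 − 331/450 = 26% loss the 331-event trigger could not be reached with 450 subjects. That test will not take place. Under the SAP the trial is exploratory, with 20 randomized subjects and descriptive Kaplan-Meier PFS. What is affected is how BICR PFS and DOR are read, where one discordant subject is 9% to 11% of an arm. The point is worth fixing because the remedy is small.

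**What to change.** 1. **Protocol 4.5 and 7.6.** Reconcile them with Table 1 note c, so that scheduled disease assessments after treatment continue until BICR progression, new anticancer therapy, death, loss to follow-up, withdrawal of consent or End of Clinical Trial, whatever the Investigator has called. Where BICR status is not returned to sites, keep the note c schedule. New anticancer therapy should remain a stop, because SAP VIII.A disregards later assessments for PFS. This concerns endpoint imaging only, not decisions on treatment.
2. **SAP Table 1.** State that assessments no longer scheduled under the protocol do not count as missed, so that a later death without new therapy is an event.
3. **SAP VIII.C.** Add one supplementary BICR PFS analysis in which Investigator progression, new anticancer therapy or death also counts as an event. Report it beside the planned Investigator PFS.

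Cost: wording in two protocol sections and one SAP table, a few 3-monthly scans that note c already schedules, and one extra Kaplan-Meier run. Items 2 and 3 need no new data and remain useful if no further scans can be obtained.
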